The protective role of recipient T cells after transplantation was not investigated in detail until recently because most transplantation protocols eradicate recipient T cells through a combination of the conditioning chemotherapy and an allogeneic effect of the graft. The notion that recipient T cells could survive even early after transplantation was supported by data from pediatric patient population undergoing UCB transplantation and showed that antigen-specific T lymphocytes of recipient origin were detected in patients receiving a transplant with a related donor, after a chemotherapy-based conditioning regimen, and who did not have GVHD(27). Recently, Chalandon et al showed when a T-cell depletion protocol was used that allowed recipient T cells to repopulate the T-cell compartment, the T cells maintained their function even after conditioning that includes total body irradiation. Furthermore, T cells appeared to protect the patient from CMV-related complications. These data support the notion to investigate the use of recipient-derived autologous CTLs for CMV reactivation after allogeneic HSCT especially for patients without the option to use donor-derived CTLs. Recently, Meij et al. showed the feasibility of generating patient-derived autologous CMV specific CTLs using IFN γ -capture system.

In conclusion, alternative strategies to provide safe and effective adoptive therapy for CMV reactivation after HSCT are needed especially in patients with CMV seronegative donors or following the use of UCB where there is no memory T cell response to CMV.

In this study, we will use this original and novel approach of infusing recipient-derived autologous CMV-specific CTLs for the treatment of CMV reactivation following HSCT in CMV seropositive patients.

Eligibility: (List All Criteria)

Inclusion:

- 1) STEP 1: Within 30 days of study entry: Patients with a history of bone marrow disorders including hematological malignancies and aplastic anemia, Myelodysplastic Syndrome (MDS) and Myeloproliferative disorder (MPD) planning to undergo allogeneic HSCT with reduced intensity or myeloablative conditioning regimens.

- 2) Disease status must be complete remission by standard criteria for Lymphoma and Acute Leukemia patients.
- 3) Patients with Myelodysplastic Syndrome (MDS) and Myeloproliferative Disorder (MPD) must have <5% blasts in the bone marrow.

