- 4) Patients with T Cell ALL must be in complete remission and MRD negative (-) by flow cytometry and molecular studies.
- 5) Patients \geq 18 years of age.
- 6) Karnofsky greater than or equal to 80%.
- 7) CMV seropositive.
- 8) Donor is either matched related, matched unrelated, mismatched unrelated, or haploidentical. Cord blood recipients are also eligible.
- 9) Hgb greater than 10 g/L.
- 10) Patient or patient's legal representative, parent(s) or guardian able to provide written informed consent.
- 11) Negative pregnancy test in female patients of childbearing potential.
- 12) STEP 2: Eligibility at time of generating and infusing CMV-specific cytotoxic T cells (adoptive immunotherapy): CMV reactivation defined as CMV DNAemia \geq 137 copies/ml.
- 13) Evidence of neutrophil engraftment defined as the absolute neutrophil count (ANC) $> 0.5 \times 10^3$ /for 3 consecutive days.
- 14) Clinical status to allow tapering of steroids to less than 0.5 mg/kg/day prednisone or equivalent.
- 15) Negative pregnancy test in female patients of childbearing potential.

Exclusion:

- 1) STEP 1: Within 30 days of study entry: T cell leukemia or lymphoma.
- 2) CMV seronegative.
- 3) Positive for HIV, HBV, HCV, HTLV1 and/or HTLV2.
- 4) STEP 2: Eligibility at time of generating and infusing CMV-specific cytotoxic T cells (adoptive immunotherapy): Documented CMV end-organ disease.
- 5) Patients receiving ATG, or Campath within 28 days of CMV reactivation.
- 6) Patients with other uncontrolled infections. For bacterial infections, patients must be receiving definitive therapy and have no signs of progressing infection for 72 hours prior to generating CTLs. For fungal infections patients must be receiving definitive systemic anti-fungal therapy and have no signs of progressing infection for 1 week prior to generating CTLs. Progressing infection is defined as hemodynamic instability attributable to sepsis or new symptoms, worsening physical signs or radiographic findings attributable to infection. Persisting fever without other signs or symptoms will not be interpreted as progressing infection.

- 7) Patients who have received donor lymphocyte infusion (DLI) within 28 days.
- 8) Patients with active acute GVHD grades II-IV.
- 9) Active and uncontrolled relapse of malignancy.

Are patients <18 years of age eligible to participate in this study? Yes No

Studies that include children must meet the criteria for inclusion.

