http://www.fda.gov/ohrms/dockets/AC/04/briefing/4028B1_05_NIH-Inclusion%20of%20Children.doc
<http://www.hhs.gov/ohrp/policy/populations/children.html>

Studies that exclude children must have appropriate justification. Please select all that apply:

Phase II or III study with no Phase I data for the drug in pediatrics.

Please provide a letter from the Sponsor stating if a Phase I study planned for patients <18 years of age. (May include file attachment)

- This is a rare disease in pediatric patients
- Our Pediatric transplant program is very small
- Our sponsor does not allow pediatric patients to be included in this study.

Are participants >65 years of age eligible to participate in this study? Yes No

Are pregnant women eligible to participate in this study? Yes No

Will the recruitment population at M. D. Anderson include persons who are incarcerated at time of enrollment (e.g., prisoners) or likely to become incarcerated during the study?

Yes No

Disease Group:

Blood And Marrow Transplantation, Leukemia, Lymphoma

Treatment Agents/Devices/Interventions:

CMV-specific CTLs

Proposed Treatment/Study Plan:

Is treatment assignment randomized? Yes No

Is this a blinded or double-blinded study? Yes No

Collection of peripheral blood mononuclear cells (PBMC) for manufacturing of CTLs

After enrollment, PBMC will be collected via venipuncture.

Venipuncture: up to 500 mL one time at the MD Anderson Blood Bank. The product will be cryopreserved for future use to generate CMV-specific CTLs.

PBMCs will be stored for 3 years. If the PBMCs are not needed to generate CTLs, they will be discarded.

Allogeneic HSCT and follow-up

1. Patients will undergo allogeneic HSCT per institutional guidelines.
2. CMV reactivation will be monitored by checking CMV DNA level by polymerase chain reaction (PCR).

Manufacture of recipient derived autologous CMV specific CTLs under GMP conditions

1. After documentation of CMV reactivation, defined as CMV DNA load is equal to or greater than 137 copies/ml, cryopreserved PBMC product of eligible patients' defined under "Eligibility" will be used for generation of CMV-specific CTLs.

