6. The first three patients on protocol will be observed for at least 28 days for safety monitoring before more patients are enrolled in the study.

Supportive care

1. All patients should receive supportive care as clinically indicated.
2. It is essential to avoid steroid as those may interfere with the efficacy of the infused CMV-specific CTLs.
3. Steroids will be given only if the patient develops a severe or life-threatening reaction to the infused CMV-specific CTLs.

Initiation of anti-viral therapy

1. CMV viral load will be monitored at least weekly by PCR within the 28 days of autologous recipient-derived CMV-specific CTL infusion.

2. Indication to initiate anti-viral therapy will be determined by their response status as described in Table 4.

Table 4. Time-table for monitoring efficacy and initiation of anti-viral drugs

Monitoring	Day 5-7	Day 12-14	Day 19-21	Day 26-28
CMV DNA increase > 50% compared with baseline	X	X	X	X
CMV DNA \geq 5000 copies/ml	X	X	X	X
CMV DNA decrease < 50% compared with baseline			X	
CMV end-organ disease	X	X	X	X
X, indication to start anti-viral therapy				

Management of potential treatment toxicity

1. Microbial contamination of T-cell product.

There is a potential that processing the T-cell product will inadvertently introduce microorganisms that could cause infection in the recipient after the cells are infused. Cultures of the T-cell product will be obtained to monitor for contamination. In the event that a microbial contamination is discovered after infusion of CTLs, standard GMP procedures will be followed.

2. Graft failure: Graft failure is initial neutrophil engraftment followed by subsequent decline in the ANC to $< 500/\text{mm}^3$ for three consecutive measurements on different days, unresponsive to growth factor therapy that persists for at least 14 days in the absence of a known cause such as relapse. GF will be monitored as clinically indicated for the first 6 months after CTL infusion.

3. Graft Versus Host Disease (GVHD)

The risk of GVHD following the infusion of recipient-derived autologous CTLs is expected to be low.

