Statistical Considerations:

Treatment and Primary Outcomes. This is a single-arm phase II trial of autologous virus specific CTLs for CMV reactivation in patients with hematologic malignancies (excluding T cell leukemia and lymphoma) undergoing CMV seronegative matched unrelated donor (MUD), mismatched unrelated or cord blood allogeneic stem cell transplant. Whole blood will be collected and frozen prior to transplant. After documentation of CMV reactivation, defined as CMV at a level ≥ 137 DNA copies/ml by PCR, autologous CMV-specific CTLs will be generated to be infused within 72 hours of CMV reactivation, if the patient has ANC engraftment, no acute GVHD or steroid administration ≤ 0.5 mg/kg dose. All outcomes will be recorded starting from the time of T-cell administration. While the dose of T-cells will vary depending on how many cells can be grown by ex vivo expansion after thawing and prior to administration, the maximum dose will be $10e5$ viable CD3+ T cells/kg. It is anticipated that 20-25 patients per year will be accrued and that approximately 2 patients per month will develop CMV reactivation and thus be eligible to receive autologous CTLs. A maximum of 36 patients will receive autologous CTLs. The two primary endpoints, starting at the time of autologous T-cell administration, will be $T =$ time to non-relapse mortality and $Y =$ [28-day success], where "success" is defined as follows. CMV will be evaluated weekly at 7, 14, 21 and 28 days using PCR. Treatment will be considered a success if the patient does not require initiation of CMV anti-viral therapy. Anti-viral therapy will be started if 1) End-organ disease is documented at any time point after CTL administration 2) Increase in CMV DNAemia $>50\%$ compared with baseline at any time point 3) Decrease in CMV DNAemia $<50\%$ compared with baseline at day 21 after CTL administration and 4) CMV DNAemia >5000 copies/ml at any time point.

Non-relapse mortality is defined as death because of causes other than relapse of the underlying hematological malignancy. Relapse of underlying hematological malignancy will be a competing event for non-relapse mortality. Time to non-relapse mortality is defined as time to non-relapse mortality from date

of stem cell transplantation.

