Sample Size. The effective sample size for evaluating CTL effects is the number of patients who suffer CMV reactivation, are eligible to receive CTLs, and actually receive CTLs, not the number enrolled and undergoing a transplant. In order to obtain a maximum of 36 patients who are treated with CTLs, assuming an accrual rate of 5 patients per month who receive a transplant and a 40% rate of patients with CMV who satisfy the entry criteria for receiving CTLs, it is expected that an effective accrual rate total of 2 patients per month will be enrolled, receive a transplant, and subsequently develop CMV. Due to the randomness of the treatable CMV subsample size, which is binomial in $q = .40$ and $n =$ number of patients initially enrolled and transplanted, up to 105 patients will be enrolled (21 months accrual) to ensure at least a 90% probability that there will be at least 36 patients with CMV. If $q = .50$, then up to 83 patients (17 months accrual) will be enrolled to ensure this same sample size with this reliability. The overall sample size of 36 will ensure that, if the trial is not stopped early and, for example, 18/36 patients achieve 28-day success, then a posterior 95% credible interval for p starting with a beta (.50,.50) prior would be .342 - .658, or approximately 34% to 66%.

The first three patients on protocol will be observed for at least 28 days for safety monitoring before more patients are enrolled in the study.

Statistical Models and Early Stopping Rules

Probability of 28-day Success. The Bayesian method of Thall and Sung will be used to monitor the $p =$ the probability of 28-day success. Assume that the number of 28-day successes $Y \sim \text{binomial}(p, 36)$ and that *a priori* $p \sim \text{beta}(.5, .5)$. The trial will be stopped early if $\text{Pr}(p > .50 \mid \text{data}) < 0.010$. Assuming a $\text{beta}(500, 500)$ prior for the standard response probability, and monitoring continuously, the trial will be stopped early if $[\# \text{ patients with 28-day success}] / [\# \text{ patients evaluated for 28-day success}]$ is less than or equal to $0/5, 1/9, 2/12, 3/15, 4/18, 5/21, 6/24, 7/26, 8/29, 9/31, \text{ or } 10/34$.

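### The 28-day safety hold counts the first three patients on protocol rather than the first three infused, gives the 28 days no start, and gates enrolment, so as written it does not secure an early look at infused patients

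*Combined protocol and SAP*

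**What the plan says.** The hold appears twice in the same words: as item 6 of Administration and Monitoring of CTL infusion, and at the end of Sample Size in Statistical Considerations. Both say "The first three patients on protocol will be observed for at least 28 days for safety monitoring before more patients are enrolled". Three other parts of the document bear on how to read it.

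- **Entry comes before transplant.** Step 1 of the inclusion criteria admits patients "planning to undergo allogeneic HSCT with reduced intensity or myeloablative conditioning regimens". The treatment plan then says "After enrollment, PBMC will be collected via venipuncture".
- **Infusion is a separate, later step.** The second block of criteria is headed "STEP 2: Eligibility at time of generating and infusing CMV-specific cytotoxic T cells". It requires CMV DNAemia of at least 137 copies/ml and "Evidence of neutrophil engraftment defined as the absolute neutrophil count" above the stated threshold.
- **The plan separates enrolled from infused patients.** Sample Size bases the evaluation of CTL effects on patients who "actually receive CTLs, not the number enrolled and undergoing a transplant". It plans on a treatable fraction of q = 0.40, with 0.50 as the alternative.

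Treatment and Primary Outcomes adds "All outcomes will be recorded starting from the time of T-cell administration". That sets a general time origin but does not mention the hold.

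**The concern.** A safety hold is useful only if the patients under observation have received the product. Here the count is of patients on protocol, the gate is on enrolment, and the 28 days have no day 0. A patient joins the protocol before transplant and may never reactivate, engraft or meet the other Step 2 criteria. Followed to the letter, the hold could be lifted with no infused patient observed. If it is read instead as three infused patients, blocking enrolment after the third patient would usually leave too few patients to satisfy it.

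At stake is the early safety look at a cell product that the rationale calls novel. No other rule shown in the document requires a period of observation in the first infused patients before the trial continues.

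**Working it through.** **Inputs.** From Sample Size: q = 0.40 (alternative 0.50), the treatable number binomial in q, 5 entries per month, 105 enrolled (83 if q = 0.50), target 36. From Treatment Failure Event: prior inverse gamma(3, 13.9) on the median m, cut-off 0.0717, reference 6.96 months. Patients are taken as independent, and every treatable patient as infused.

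**1. The plan's own figures.** P(X ≥ 36) with n = 105, q = 0.40 is 0.903 (n = 104 gives 0.890). With n = 83, q = 0.50 it is 0.906 (n = 82 gives 0.888). Both stated sizes reproduce, so the binomial model is the plan's own.

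**2. Infused patients among the first three enrolled.** P(k) = C(3,k) q^k (1−q)^(3−k), with unlimited follow-up:

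| k infused | q = 0.40 | q = 0.50 |
|---|---|---|
| 0 | 0.6³ = 0.216 | 0.125 |
| 1 | 0.432 | 0.375 |
| 2 | 0.288 | 0.375 |
| 3 | 0.4³ = 0.064 | 0.125 |

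The expected number infused is 3q = 1.2 or 1.5. If the 28 days run from study entry, 0.216 and 0.125 are lower bounds for observing no infused patient, because transplant, engraftment and reactivation must all come first.

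**3. Three infused patients required, enrolment stopped at three.** P(fewer than three infused) = 1 − 0.064 = 0.936 at q = 0.40, and 1 − 0.125 = 0.875 at q = 0.50. The hold could then not be completed.

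**4. Enrolment needed for three infusions.** The mean is 3/q = 7.5 at q = 0.40 and 6 at q = 0.50. For a 90% chance, n = 12 (0.917) or n = 9 (0.910). These ignore the lag from enrolment to infusion and so are minimum figures. The documents do not give that lag. The table comes from a simulation with Poisson entry at 5 per month, q = 0.40, a gamma lag (shape 4) of assumed mean, and enrolment paused at the third infusion:

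| Assumed mean lag (months) | 0.5 | 1 | 2 | 3 |
|---|---|---|---|---|
| Mean enrolled before the pause | 9.9 | 12.4 | 16.9 | about 21 |
| Mean further infusions in the next 28 days | 0.98 | 1.48 | 1.62 | 1.51 |

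Treatment and Primary Outcomes gives 20 to 25 patients per year beside about 2 reactivations per month. Two per month is 24 per year, so I read 20 to 25 as treated patients. Dividing by 0.40 gives 50 to 62.5 entries per year, or 4.2 to 5.2 per month. Over that range further infusions run from about 0.8 to 1.7.

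**5. Whether the other rules fill the gap.** The response rule cannot stop before 0/5. For the failure rule, one event with zero follow-up gives m ~ inverse gamma(4, 13.9). Pr(m > 6.96) is then the probability that a Gamma(4, 1) variable is below 13.9/6.96 = 1.997, which is 0.142. Follow-up time only raises it. A single failure event among the first three infused therefore cannot reach 0.0717.

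**The case against.** The strongest reply is that the intended meaning is plain. Item 6 stands under a heading about CTL infusion, directly after the dose, and outcomes are recorded from T-cell administration. On that view, 28 days from infusion in the first three infused patients is the natural reading, and 0.216 describes a hold that nobody would run. The reply is right about probable intent, and it makes this a drafting gap. It does not rescue the rule, because the intended reading meets the 0.936 problem as long as enrolment stops at three.

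A second reply is that the failure rule runs continuously on infused patients. Example 1 under Stopping Rules stops on three events by day 25 among four patients, and a protocol-specific monitoring plan is cited but not shown. This oversight is real. It sets no stated observation period, and one event cannot trigger the failure rule.

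A reader might go further and infer that the sponsor meant to clear the product on uninfused patients, or that early safety is otherwise unprotected. The heading of item 6 and the continuous failure rule speak against both.

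**Conclusion.** The point holds as a defect in how a safety rule is worded, and it should be corrected. Taken literally, the hold has a chance of at least 0.216 at q = 0.40 (0.125 at q = 0.50) of ending with no infused patient observed if its clock starts at entry. Taken as probably intended, with enrolment capped at three, it fails to reach three infused patients with probability 0.936 (0.875). These figures rest on the plan's q, on independence, and on every treatable patient being infused. A product that failed release or missed the 72-hour window would make them worse.

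It would be wrong to infer that the sample size is affected: 105, 83 and 36 stand. Nor does the correction introduce the 28-day pause, which the current text already contains.

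**What to change.** Replace the sentence in both places with: *Enrolment stays open until three patients have been infused with CTLs; it then pauses until each of the three has been observed for at least 28 days after infusion.* State as well whether patients already enrolled may be infused during the pause.

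**Cost of the change.** Enrolment pauses later, so more patients give blood before the safety look: at least 7.5 on average at q = 0.40, and about 10 to 21 at 5 entries per month for an assumed mean lag of 0.5 to 3 months, against 3 as written.

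**Cost of the choice about infusions.** If infusions continue, about 1 to 1.7 more are expected during the 28 days at about 5 entries per month. If they are also paused, the 72-hour window means that patients who reactivate in that time lose treatment. P(at least 36 treated) from 105 enrolled then falls from 0.903 to 0.864 if one is lost, or 0.815 if two are. Either choice is defensible, and the sponsor should state which applies.

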THE UNIVERSITY OF TEXAS

Protocol Abstract Page

The Pre-emptive Use of Recipient-Derived Autologous CMV-Specific Cytotoxic T Cells for CMV Reactivation After Allogeneic Stem Cell Transplantation.

2013-0620

Core Protocol Information

Study Chairman:	[name]
Department:	Stem Cell Transplantation and Cellular Therapy
[contact]
Unit:	423
Full Title:	The Pre-emptive Use of Recipient-Derived Autologous CMV-Specific Cytotoxic T Cells for CMV Reactivation After Allogeneic Stem Cell Transplantation.
Protocol Phase:	Phase II
Version Status:	Terminated 05/14/2019
Version:	11
Document Status:	Final

Abstract

Objectives:

Primary

1. To assess the efficacy of recipient-derived autologous cytomegalovirus (CMV)-specific cytotoxic T cells (CTLs) as a pre-emptive therapy for CMV reactivation after allogeneic hematopoietic stem cell transplantation (HSCT) from a CMV negative donor.
2. To assess the non-relapse mortality with the use of recipient-derived autologous cytomegalovirus (CMV)-specific cytotoxic T cells (CTLs) as a pre-emptive therapy for CMV reactivation after allogeneic hematopoietic stem cell transplantation (HSCT) from a CMV negative donor.

Secondary

1. To assess the safety of the pre-emptive use of recipient-derived autologous CMV- specific CTL as a pre-emptive therapy for CMV reactivation after HSCT.
2. To assess functionality and persistency of infused autologous CMV-specific CTLs.

Rationale: (Be as concise as possible)

CMV is a B-herpesvirus that is very common in humans and leads to asymptomatic infection followed by viral persistence and latency. CMV is still one of the major causes of infectious complications after HSCT, although several new prophylactic options for CMV infection/disease have been made available. Among the recipients of HSCT, CMV causes pneumonia, gastroenteritis, and less commonly retinitis and hepatitis. Because of the initial high mortality of CMV pneumonia (80-90%), transplant physicians have long sought strategies to reduce its morbidity and mortality. CMV also exhibits an immunosuppressive

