The Department of Biostatistics Clinical Trial Conduct (CTC) website will be used to monitor the time to non-relapse mortality, and the trial conduct will be implemented by a Statistical Analyst from the Biostatistics Department.

The Clinical Trial Conduct website is an MD Anderson portal for multi-center trials that provides treatment assignment, randomization, and monitoring for several hundred trials. The website was developed and is maintained by software developers in the Biostatistics department. There are approximately 7 different randomization algorithms implemented at the site, covering methods from simple randomization to innovative adaptive randomization. The trials and statistical details are overseen by the statisticians in the MD Anderson Biostatistics department. Users of the website (nurses, clinicians, etc) are registered on specific trials at the site and may be granted various levels of access (read only, write, blinded, etc).

BMTWeb is departmental clinical research application used to collect patient treatment data for patient receiving transplant in SCTCT department. It operates as a data repository for the clinical data transmitted to CIBMTR to meet our patient follow up requirements.

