Treatment Failure Event. Treatment failure event is defined as death, graft failure, or grade 3-4 toxicity secondary to CTL infusion in 6 months after CTL infusion. The Bayesian method of Thall, et al. will be used to monitor non-relapse mortality (regimen-related death, RRD). Assume that $T \sim \text{exponential}$ with median m , and that *a priori* $m \sim \text{inverse gamma}(3, 13.9)$, which has mean 6.96, corresponding to historical probability $\text{Pr}(T < 6 \text{ months}) = 0.45$. The trial will be stopped early if $\text{Pr}(m > 6.96 \text{ months} \mid \text{data}) < 0.0717$. In terms of median of T , the early stopping event is $[m > 6.96 \text{ months}]$, which is equivalent to $[\text{mean}(T) > 10.04 \text{ months}]$ because T follows an exponential distribution.

Early Deaths. If a patient treated for CMV dies from any cause before day 28, or drops out for some reason, that will be counted as a failure when scoring 28-day success. Due to the lack of computer software to jointly model the two different types of death, regimen-related and not regimen-related, which are competing risks, and non-fatal 28-day failure, and implement a design which separates these events, if a death within 28-days is regimen-related, then the design will "double count" the event. Specifically, such a death will be scored as an event in the monitoring rule for m and also as a 28-day failure in the monitoring rule for p . Consequently, the monitoring rules are conservative. It is anticipated, however, that the actual probability of such very early deaths will be very small, so these considerations will not substantively affect trial conduct.

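### One stopping rule (median 6.96 months, 0.45 at 6 months, cut-off 0.0717) is tied to two different events: non-relapse mortality, and a composite that adds graft failure and grade 3-4 toxicity

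*Combined protocol and SAP*

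**What the plan says.** All references are to the combined protocol and SAP.

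**Passages that make the event non-relapse mortality (NRM) or death**
- Objectives, Primary 2: "To assess the non-relapse mortality with the use of recipient-derived autologous cytomegalovirus".
- Treatment and Primary Outcomes: one primary endpoint "will be $T =$ time to non-relapse mortality". The same section adds: "Non-relapse mortality is defined as death because of causes other than relapse of the underlying hematological malignancy". Relapse is named as a competing event.
- The paragraph on the Clinical Trial Conduct website: it "will be used to monitor the time to non-relapse mortality".
- Treatment Failure Event, second sentence: the Bayesian method "will be used to monitor non-relapse mortality (regimen-related death, RRD". The model that follows is for T, with a prior on its median "which has mean 6.96, corresponding to historical probability" of 0.45 for T below 6 months.
- Early Deaths, on a regimen-related death within 28 days: "such a death will be scored as an event in the monitoring rule for m".
- Table 7: the scenario column and the stopping column for this rule are both labelled by death.

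**Passages that make the event a composite**
- Treatment Failure Event, heading and first sentence: "Treatment failure event is defined as death, graft failure, or grade 3-4 toxicity secondary to CTL infusion in 6 months after CTL infusion".
- Stopping Rules: the instruction to stop accrual is stated for the treatment failure time event, with the same 6.96 and 0.0717.
- The worked examples under Stopping Rules: each patient contributes the time of a failure event or the current follow-up.

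There is one prior, one benchmark and one cut-off. No sentence says that there are two rules.

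**The concern.** The rule depends on the data only through the number of events (Nevents) and the total follow-up time (TFU), so what counts as an event decides the outcome. The two definitions disagree on non-fatal graft failure and on grade 3-4 toxicity secondary to CTL infusion. They may also disagree on relapse death: NRM excludes it, whereas the composite says only death, unless the qualifier about CTL infusion is read as covering all three components.

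A benchmark is meaningful only for the event it describes. If 0.45 is a historical NRM rate and composite events are counted against it, an acceptable treatment is stopped too readily. If 0.45 is a composite rate and only NRM is counted, the rule is too lenient.

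This matters more than usual here. The protocol assigns no data safety monitoring board and schedules no interim analysis, and it gives continuous monitoring under the statistical design as the reason for the latter.

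**Working it through.** **1. The benchmark.** Inputs from Treatment Failure Event: exponential T with median 6.96 months; prior inverse gamma(3, 13.9).
- Pr(T < 6) = 1 − 2^(−6/6.96) = 0.4498, stated as 0.45.
- Mean of T = 6.96/ln 2 = 10.04 months, as stated.
- Prior mean of m = 13.9/(3 − 1) = 6.95, stated as 6.96.

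The figures agree with each other. They do not show which event they describe.

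**2. The worked examples.** With TFU in 30-day months, the posterior m | data ~ inverse gamma(3 + Nevents, 13.9 + TFU) gives Pr(m > 6.96 | data) = P(3 + Nevents, (13.9 + TFU)/6.96), where P is the regularised lower incomplete gamma function.
- Example 1: TFU 170/30 = 5.667, argument 19.567/6.96 = 2.811, Nevents 3: 0.0661 (stated 0.066).
- Example 2: TFU 220/30 = 7.333, argument 21.233/6.96 = 3.051, Nevents 3: 0.0891 (stated 0.089).
- Example 3: TFU 305/30 = 10.167, argument 24.067/6.96 = 3.458, Nevents 4: 0.0621 (stated 0.062).

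All three are reproduced. If m is a median, TFU would be multiplied by ln 2, which gives 0.046, 0.059 and 0.034 and does not match. That is a separate question. I use the form that matches the protocol's own figures.

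**3. One event reclassified, TFU held fixed, cut-off 0.0717**

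| Example | Nevents | Probability | Decision |
|---|---|---|---|
| 1 | 3 → 2 | 0.066 → 0.154 | STOP → do not stop |
| 2 | 3 → 4 | 0.089 → 0.036 | do not stop → STOP |
| 3 | 4 → 3 | 0.062 → 0.137 | STOP → do not stop |

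Holding TFU fixed does not create these reversals. In this posterior more follow-up raises the probability, as Examples 1 and 2 show with three events each. A patient whose event is not counted would go on adding follow-up, which moves the result further in the same direction.

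**4. 0.45 is an NRM rate but composite events are counted.** The documents give no rate for non-fatal graft failure or CTL-related grade 3-4 toxicity. I assume that a further x = 5, 10 or 20% of patients have such an event by 6 months, independently of NRM. The composite 6-month rate is 1 − 0.55(1 − x) = 0.478, 0.505 or 0.560.

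Simulation: 36 treated patients at 2 per month (both from the protocol); NRM exponential with Pr(T < 6) = 0.45; added events uniform on 0 to 6 months and counted if before death; a look at every event; 6 months' further follow-up; 20,000 runs.

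| Set-up | x = 0 | 5% | 10% | 20% |
|---|---|---|---|---|
| Follow-up not capped | 0.077 | 0.108 | 0.141 | 0.235 |
| Events and TFU capped at 6 months | 0.080 | 0.109 | 0.145 | 0.258 |

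Folding the added events into a single exponential hazard and varying the look times (4,000 runs) gives 0.07–0.08 rising to 0.09–0.10, 0.12–0.15 and 0.24–0.29.

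Check against Table 7's death-rule column (0.100, 0.374, 0.648 at 0.45, 0.60, 0.65): the simulation gives 0.077, 0.432, 0.659 uncapped and 0.080, 0.392, 0.590 capped. The agreement is approximate only.

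**5. 0.45 is a composite rate but only NRM is counted.** The matching NRM benchmark would be 1 − 0.55/(1 − x) = 0.421, 0.389 or 0.312 for the same x. Holding NRM to 0.45 is then too lenient.

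**The case against.** The strongest reply is that the rule does say what it monitors. T is defined as time to NRM, the method sentence and the website text repeat this, and Early Deaths scores regimen-related death for m. On that reading relapse death is already excluded, and the composite side amounts to one definition sentence plus labels. This largely stands, and it is why NRM is the better-supported event. It does not remove the conflict. The composite is defined in the rule's own paragraph, and the instruction to stop accrual names treatment failure. An analyst who follows NRM leaves that definition without a rule; one who follows the composite contradicts the definition of T, the website text and Early Deaths. Table 7 does not settle it: death argues against the non-fatal components but does not identify NRM.

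Three further objections limit the size of the point.
- The examples have four to seven patients and sit beside the cut-off, so any one-event change reverses them. They show that a decision can change, not how often it would. This stands.
- A reader might infer that counting composite events always stops the trial more often than Table 7 states. The documents do not support that. At 5% added events the simulated 0.09 to 0.11 is about equal to Table 7's 0.100. A clear excess needs 10 to 20%, and nothing in the documents shows such rates to be likely: only toxicity secondary to CTL infusion counts, and the toxicity section's definition of graft failure excludes a known cause.
- A reader might also infer that 0.45 has no source. The document is a protocol abstract whose table numbering begins at 4 and which cites a numbered reference without a list, so the source may lie in text not available here. What can be asked is confirmation that 0.45 belongs to the chosen event.

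**Conclusion.** The contradiction is real and lies in the current text. One rule, with one benchmark and one cut-off, is attached to two events, and the passages cannot all be followed. NRM is the better-supported reading.

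That a stopping decision can turn on the choice follows from the protocol's own examples and needs no outside assumption. How often it would turn is uncertain. If 0.45 is NRM and composite events are counted, false stopping rises from about 0.08 to about 0.11, 0.14 or 0.25 at 5, 10 or 20% added events. This rests on assumed rates, independence from NRM and a simulation that only approximates Table 7. In the opposite mismatch the rule is too lenient.

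A reader might go further and infer that the trial was run on the wrong event, or that its termination reflects this. The documents do not say which event was entered in the monitoring software, and they do not link the terminated status to this rule. They support only that any account of how the rule was applied must name the event counted.

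**What to change.** - Reconcile Treatment and Primary Outcomes, the conduct-website paragraph, Treatment Failure Event, Early Deaths, Table 7 and Stopping Rules with its examples to one named event. The choice is the sponsor's.
- State whether non-fatal graft failure and CTL-related grade 3-4 toxicity count in Nevents. If the composite is kept, state also whether relapse death counts.
- Confirm that 0.45 is the historical rate of that same event, and relabel Table 7 to match.
- If NRM at 0.45 is confirmed, Table 7 needs no re-run, because its death-rule column depends on the event probability and not on the event's name.
- If the composite is chosen or the benchmark changes, reset the prior and cut-off to the historical rate of the chosen event and re-run Table 7.

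The cost is wording and possibly one re-run, whose stopping probabilities may be less favourable. Choosing NRM leaves graft failure and CTL-related toxicity outside this rule; choosing the composite requires a historical rate for it.
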